COVER PAGE

OFFICIAL TITLE OF THE STUDY: PREVENTING DRUG USE AND RISK BEHAVIORS IN ADOLESCENT GIRLS

BRIEF TITLE: SAFE, HEALTHY, ADOLESCENT RELATIONSHIPS AND PEERS (SHARP-TEEN)

NCT NUMBER: NCT02420548

DATE OF DOCUMENT: JANUARY 21, 2019

STUDY PROTOCOL WITH SAP

Brief Summary

Initiation of drug use and participation in sexual-risk behaviors such as having multiple sexual partners, unprotected sexual intercourse, and intercourse with drug users are all too common among female youth with involvement in the child welfare or juvenile justice system. Studies consistently find that these youth have disproportionately higher rates of these problems that, in addition to increasing risk for negative outcomes, have other costly sequelae such as drug addiction, early pregnancy, sexually transmitted infection, HIV contraction, delinquency, and early mortality (e.g., Santelli et al., 2001; Stueve et al., 2005). The goal of this study, which is Research Component 2 within a P50 Center Grant, is to prevent drug use and sexual-risk behaviors in 13–18 year-old girls with early adverse life experiences such as maltreatment ($n = 123$) through the development and evaluation of a preventive intervention.

- 1. To Examine the Effects of the SHARP (Safe, Healthy, Adolescent Relationships and Peers) Intervention on the Developmental trajectories of Drug Use, Sexual-Risk Behaviors, and Delinquency.** We will examine outcomes at intervention termination (approx. 6 months) and a 12-month follow-up using quantitative analysis methods.
- 2. To Examine Mediating Processes Linking the Intervention with Developmental Trajectories of Drug Use, Sexual-Risk Behaviors, and Delinquency.** We will examine two sets of mediators, directly targeted in our intervention: a) improvement in parenting practices, including positive reinforcement, limit setting, and supervision; and b) improvements in the girls' relationships and skills, including peer and partner relations, refusal skills, and goal setting skills. Analyses will focus on whether these two domains partially mediate the effects of the SHARP intervention on the developmental outcomes. Trajectories of drug use, sexual-risk behaviors, and delinquency will be examined separately, and together, in relation to the two proposed sets of mediators.

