Assessment. Data will be collected through three 2-hour in-person interviews with the teenage girl and her primary caregiver. The interviews will take place either at the participant's home or at the university research center, whichever is most convenient for the participant. The first interview (baseline) will be scheduled immediately after recruitment. The second two interviews will occur 6- and 12- months after the baseline interview, respectively. The caregiver and youth interviews will consist of self-administered questions on a computer and interviewer-administered questions. For the drug use and sexual-risk behavior questions, the interviews and questionnaires have skip patterns, such that youth who report never engaging in any drug use (or sexual-risk behavior) are not asked the follow-up questions about frequency, etc. A short, 10-minute discussion activity involving the teen and her caregiver will be videotaped at the 6-month assessment. Child welfare records pertaining to incidents where the youth participant was reported to be a victim of child maltreatment or neglect will be requested from the State of Oregon. Staff will also collect juvenile court information about the girl from the Department of Youth Services. At the 12-month interview, the teen will provide a urine specimen for a urinalysis (UA). The UA will reveal the presence or absence of a class of drugs in the urine specimen and a second assay will be completed for a subset of youth at the [name] Laboratory at Children's Hospital Los Angeles (CHLA) to measure isoprostane levels (a measure of oxidative stress).

Intervention. Three intervention groups will be conducted per year (7-8 caregivers per parenting group), held on a rolling basis. Girls will be randomly assigned to intervention or control conditions during the baseline assessment home visit, where caregivers will be presented with two sealed, blank envelopes from which to choose. A slip of paper in the envelope will determine study condition (the randomization procedure will target blocks of 20, representing 10 girls in SHARP and 10 corresponding control girls; 10 pieces of paper labeled "SHARP group" and 10 pieces of paper labeled "Usual Services" will be placed in 20 separate unlabeled envelopes).

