Analysis Approach. We will rely primarily upon latent growth modeling (LGM) using Mplus 6.12 (Muthén & Muthén, 1998-2010) and the *r* statistical package to take advantage of the longitudinal nature of the study design. The description below presents specific examples of analyses that will be used to test each Aim. Note that demographic characteristics, intervention dosage, caregiver type (foster, biological), and sample (DYS or other) will be included in models as control variables. Early adversity will be included as a covariate. We will use an intent-to-treat approach to all analyses, including all participants in their randomly assigned intervention group, regardless of how many sessions were received.

Aim 1. To Examine the Effect of the SHARP intervention on the Developmental trajectories of Drug Use, HIV-Risk Behaviors, and Delinquency. We hypothesize that girls in the SHARP intervention will show significantly lower levels of drug use, HIV-risk behaviors, and delinquency during follow-ups than the girls in the services-as-usual (SAU) condition. We will test intervention effects using a latent growth modeling (LGM) approach, whereby we will examine group differences in the slope of developmental trajectories of each outcome across T1–T3, controlling for factors described above. As an example, we will examine a two-factor LGM (the intercept and slope) of marijuana use across baseline (T1) through the 12-month follow-up (T3). We hypothesize that the SHARP girls will show significantly lower levels of growth in marijuana use over time than the SAU girls. LGM offers the advantage of testing both the longer-term effects of the SHARP intervention and also to model developmental trajectories. Our assessment includes the same measures at every wave and data are thus particularly well-suited to LGM analyses. Parallel models will be used to examine developmental trajectories of each substance (alcohol, tobacco, marijuana, and all other illicit drugs), HIV-risk behaviors, and delinquency, as well as their co-occurrence.

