Aim 2. To Examine Mediating Processes of the Developmental Trajectories of Drug Use, HIV-Risk Behaviors, and Delinquency. This Aim addresses two domains of mediating processes that lead to drug use, HIV-risk behaviors, and delinquency in girls with risk histories. A latent variable model will be used to test the hypothesis that caregivers' parenting practices at T2 mediate the SHARP intervention effect on outcomes at T3. We hypothesize that intervention effects will be significantly related to outcomes (drug use, HIV-risk behaviors, delinquency) at T3 directly and indirectly through parenting behaviors at T2. By comparing the path weights, this test will also allow us to understand the relative strength of immediate and longer-term

intervention effects. All three sets of outcomes (drug use, HIV-risk behaviors, delinquency) will be tested for each of the two hypothesized mediating process separately and simultaneously. In addition, both mediating processes can be examined simultaneously in the model. In the course of these mediational models, we will also examine main effects of the intervention on the mediators.

Aim 3. To Examine the Influence of Girls' Knowledge and Comfort Around Safe Behaviors on Her Drug Use and HIV-Risk Behaviors. We expect moderation of intervention effects by girls' knowledge about safe sex practices, her knowledge of drug use risks and norms, and her comfort talking about safe sex practices. We expect that significant intervention effects on drug use and HIV-risk behaviors will vary depending on girls' level of knowledge and comfort. Lack of knowledge and lack of comfort are expected to potentially reduce intervention effects. The direct effect model can be expanded to test the potential moderating effects of girls' knowledge of safe sex practices and drug use risks and norms.

Aim 4 (exploratory). Indices of brain maturation will be added to the analyses described in Aim 1 to examine the main effect and interaction of brain maturation on intervention outcomes for the three sets of outcomes (drug use, HIV-risk behaviors, delinquency).

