Power. In line with the results of our previous work on girls, we expect a medium effect size for the proposed intervention. Power analyses were conducted for two key models to determine whether the proposed sample size ($N = 123$) would be sufficient to detect the hypothesized effects with alpha set at .05 and power of at least .80 (Cohen, 1988). We conducted Monte Carlo simulations in Mplus (Muthén & Muthén, 2002) based on the LGM pictured using 5,000 draws with $\alpha = .05$. We used an estimate of 10% missing data across time in Aim 1. For a medium effect size ($d \approx .45$), all resulting values for the parameter bias ($< 10\%$), standard error bias ($< 10\%$), and coverage ($< .5\%$) satisfied the recommended criteria (Muthén & Muthén, 2002). Furthermore, power to detect intervention effects on the slope factor was .81. We conducted another Monte Carlo analysis to examine power for the mediated model described in Aim 2 including the four control variables listed above. Again, five thousand draws, assuming medium effect sizes (coefficient range = .4–.45) with 10% missing data over time were specified to ensure robustness of the results. All values for the parameter bias, standard error bias, and coverage satisfied the recommended criteria (Muthén & Muthén, 2002) and power to detect direct and indirect intervention effects ranged from .81 to 1.00 in the model. Thus, even though our sample size is modest, current power analyses suggest that it will be sufficient to test all hypothesized models (detect medium effect sizes with power of at least .80).

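### The Aim 2 mediation model names neither the baseline mediator nor the baseline outcome, so stable family differences can bias the parenting-to-outcome path and the indirect effect

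*Combined protocol and SAP*

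**What the plan says.** The Brief Summary frames the Aim 2 mediators as change: "improvement in parenting practices, including positive reinforcement, limit setting, and supervision", with a parallel set for the girls' relationships and skills. The Statistical Analysis Plan, under Aim 2, turns this into a model in which caregivers' "parenting practices at T2 mediate the SHARP intervention effect on outcomes at T3", with a direct path and an indirect path. No T1 term is named.

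The covariates for all models are set under Analysis Approach: "demographic characteristics, intervention dosage, caregiver type (foster, biological), and sample (DYS or other) will be included in models as control variables". Early adversity is added as a further covariate. The Power section describes its second simulation as the "mediated model described in Aim 2 including the four control variables listed above". Neither list contains T1 parenting, T1 girl skills or the T1 level of any outcome.

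Two statements bear on how firm this is. Analysis Approach introduces the models with "The description below presents specific examples of analyses that will be used to test each Aim", so the plan does not exclude T1 terms; it is silent. Under Aim 1 it says "Our assessment includes the same measures at every wave", so T1 values should generally be available.

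**The concern.** A mediation claim needs two links: arm to mediator (a) and mediator to outcome (b). Randomisation secures the first and the total effect. It does not secure the second, because nobody is randomised to a level of T2 parenting.

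Families that supervise closely at entry probably have girls who already use fewer drugs and take fewer risks. If both traits are stable, T2 parenting predicts T3 outcomes even when changing parenting does nothing. That spurious link is multiplied by the arm effect on parenting to give a spurious indirect effect. If the arm does not move parenting, the indirect effect is not biased, although b still is.

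What is at stake is the mechanism claim that SHARP works through parenting or skills. It could be overstated, or made when only entry-level differences are at work. A T2 level also does not measure the improvement that the aim describes. Aim 1 is not affected, since its growth model uses T1.

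**Working it through.** **The plan's own figure.** The Power section gives power of .81 to 1.00 for the direct and indirect effects, with coefficients of .4-.45, N = 123 and 10% missing data. It gives no loadings, residual variances or stabilities, so the figure can be neither reproduced nor refuted. Closed forms bracket it:

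- Arm effect read as a mean difference in SD units: power = Φ(d·√(N/4) − 1.96). At N = 123 this is .60 (d = .40) and .70 (d = .45). At N = 111 (10% missing) it is .56 and .66.
- Arm effect read as a standardised path, jointly with b: .995 to 1.00.

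**Model for the bias.** Let M1 and M2 be parenting at T1 and T2, and Y1 and Y3 the outcome at T1 and T3. M1 and Y1 have unit variance, and M2 has unit variance within arm.

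- M2 = a·arm + sM·M1 + error
- Y3 = sY·Y1 + b·M2 + error
- corr(M1, Y1) = r

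Without T1 terms, the estimated path converges to b + sM·sY·r, and the indirect effect is off by a·sM·sY·r.

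**Inputs.** From the documents: N = 123, 1:1 allocation (62/61 here), alpha .05, and a = .45 from the stated coefficient range. Assumed, because the documents give none: r, sM and sY, in three sets. The rates come from simulation with 10,000 replicates per scenario, ordinary least squares on observed scores and a joint-significance test, with no dosage term and no missing data.

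| | Weak | Middle | Strong |
|---|---|---|---|
| r / sM / sY | -.2 / .5 / .5 | -.3 / .6 / .5 | -.4 / .7 / .6 |
| Shift in b = sM·sY·r | -.050 | -.090 | -.168 |
| Shift in indirect effect (× .45) | -.023 | -.041 | -.076 |
| False mediation, true b = 0, no T1 terms | 6% | 11% | 32% |
| Same, arm does not shift parenting | 0.4% | 0.7% | 2.1% |
| Same as row 4, one listed covariate carries half of r: b | -.03 | -.05 | -.09 |
| and false mediation | 4% | 6% | 13% |
| True b = -.3, no T1 terms | -.35 | -.39 | -.47 |
| Overstatement (shift ÷ .3) | 17% | 30% | 56% |
| True b = -.3, both T1 terms, reliability .8 | -.30 | -.31 | -.31 |

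With true b = 0 and both T1 terms measured without error, b is 0 and false mediation is 4-5% in all three sets.

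**Why both terms.** With error-free T1 scores, either term alone removes the bias. With T1 reliability of .7 in the strong set, it does not:

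- T1 mediator only: (−.168 + .7·.24·.7) / (1 − .49·.7) = −.0504/.657 = −.08, false mediation 9%.
- T1 outcome only: −.0504 / (1 − .28²·.7) = −.0504/.945 = −.05, false mediation 7%.
- Both: −.02, false mediation 5%.

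**Precision.** Power for the arm effect on parenting is .70 without T1 terms. With T1 terms at reliability .8 it is .78/.82/.88, and .81/.87/.94 if T1 is error-free.

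**The case against.** - **The plan speaks of trajectories.** Both the Brief Summary and the Aim 2 heading do, the team relies mainly on growth models over T1-T3, and the models are offered as examples. A T1-T3 trajectory contains the T1 outcome. With the T1 outcome alone at reliability .7, false mediation is only about 4% to 7%. This leaves room for a T1-based model, but the one Aim 2 model described uses the outcome at T3. As it stands, the choice could be made after the results are seen.

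- **The rates do not describe the planned model, which includes dosage.** This stands. Assume that controls have zero dosage, that SHARP attendance averages 75% (SD 25%), and that the effect does not depend on dosage. Power for the arm-to-parenting path then falls to about .16 and false mediation to about 2%/3%/7%. With 60% (SD 35%) the rates are about 3%/5%/14%. They fall because dosage nearly duplicates arm and weakens that test, which is a separate problem. The bias in b is unchanged.

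- **The size rests on assumed correlations.** Also true. The weak set is close to nominal, and early adversity, demographics, caregiver type and sample may absorb part of the effect. None of them measures T1 parenting or T1 risk behaviour.

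- **Outcomes may not be continuous and normal.** The interviews have skip patterns for girls who report no use, so the exact rates may not carry over.

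- **Latent models are costlier than observed-score regressions at N = 123.** This is fair. Full T1 latent measurement models were not simulated.

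**Conclusion.** The concern holds. The Aim 2 model as written leaves the non-randomised mediator-to-outcome path open to baseline confounding that data already collected could reduce. The bias in b equals the product of the two stabilities and the T1 correlation: -.05 to -.17 over the assumed range, or 17% to 56% of a true path of -.3. False mediation ranges from near nominal to 32% without dosage in the model, and is lower with dosage or with informative listed covariates. The direction and mechanism are firm for a T1 correlation in the expected direction. The size is not, because the documents give no correlations and the calculation uses continuous observed scores. This is a change that should be made to the mechanism analysis. It does not touch the Aim 1 effect.

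**What to change.** 1. In each Aim 2 model, enter the T1 mediator and the T1 outcome as predictors of both the T2 mediator and the T3 outcome, wherever a T1 counterpart exists.
2. Some indicators are collected at one wave only: the "discussion activity involving the teen and her caregiver will be videotaped at the 6-month assessment", and "At the 12-month interview, the teen will provide a urine specimen for a urinalysis". For these, use the T1 report of the same construct.
3. If T1 latent measurement models are too large for N = 123, use observed T1 composites.
4. Re-run the Aim 2 power simulation with this model.
5. State that T1 adjustment does not remove unmeasured or time-varying confounding of the mediator-to-outcome path.

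The cost is SAP wording and one simulation, with no new data collection. A single-mediator, single-outcome model gains two predictors per equation. The simultaneous models gain up to five (two mediators plus three outcome sets). At reliability .8, going from two to five T1 terms lowers power for the arm effect on parenting from .78/.82/.88 to .77/.82/.87. Power for a true indirect effect (b = -.3) goes from .71/.72/.78 to .69/.70/.76, against roughly .7 with no T1 terms. Those last figures depend on how the residual variance of the outcome is scaled; the alternative scaling gives higher values with T1 terms (.74/.76/.84 with two). In neither case do the T1 terms cost material power.

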- 3. To Examine the Influence of Girls' Knowledge and Comfort Around Safe Behaviors on Her Drug Use and Sexual-Risk Behaviors.** Our prior work with girls in the juvenile justice system indicates that they have poor knowledge about safe sex practices and the effects of drugs. Further, a lack of comfort talking about safe sex practices exacerbated the odds contracting a sexually-transmitted infection (Leve et al., 2013). In this Aim, we will examine the role that comfort in discussing safe behaviors and knowledge about safe sex and drug use behaviors has on moderating the intervention effect on trajectories of drug use and sexual-risk behaviors.
- 4. (Exploratory). To Examine Whether Brain Development Moderates the Effect of the Intervention on Developmental trajectories of Drug Use, Sexual-Risk Behaviors, and Delinquency Observed in Aim 1 (above).** We will employ indices of structural and functional brain development as identified in previous studies (Bloch et al. 2013; Dosenbach et al., 2010) in a subset of 25 participants, in order to identify potential salient neurodevelopmental moderators of treatment outcomes.

Study Protocol

Recruitment and retention. The sample will consist of 123 girls between the ages of 13 and 18 and her primary caregiver (123 primary caregivers). Girls will be eligible if they are: (a) female; (b) age 13–18 years at enrollment; (c) reside in Lane County and within 70 miles of the University of Oregon at the time of enrollment; (d) have a current caregiver; (e) and both girl and caregiver are fluent in English. Girls will not be eligible for the study if they (a) are medically fragile; (b) have a significant developmental disability; or (c) have graduated from high school or have a GED. The sample will be recruited in three annual cohorts, with approximately 40 participants each year (~20 intervention, ~20 control/year). A subset of 25 girls in the full sample will be drawn from the final cohort to complete an MRI assessment to address Aim 4.

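### Aim 4 tests brain maturation by arm with age adjusted for at most as a main effect, so a brain-by-arm interaction could reflect age

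*Combined protocol and SAP*

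**What the plan says.** The Aim 4 paragraph of the Statistical Analysis Plan is one sentence. It takes the Aim 1 models and adds brain indices in order to "examine the main effect and interaction of brain maturation on intervention outcomes for the three sets of outcomes". The Brief Summary labels the aim exploratory and describes the moderator as "indices of structural and functional brain development as identified in previous studies". The stated purpose is "in order to identify potential salient neurodevelopmental moderators of treatment outcomes".

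Under Recruitment and retention, girls are eligible if "age 13–18 years at enrollment", and "A subset of 25 girls in the full sample will be drawn from the final cohort to complete an MRI assessment". The ages of those 25 girls are not given separately.

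Under Analysis Approach, "demographic characteristics, intervention dosage, caregiver type (foster, biological), and sample (DYS or other) will be included in models as control variables". Age is not named, but it would normally be one of the demographic characteristics. These are controls, not interactions with arm. The same section warns that "The description below presents specific examples of analyses that will be used to test each Aim". No section mentions an age-by-arm term, an age-adjusted brain index, or a sensitivity analysis that separates age from maturation.

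**The concern.** A maturation measure taken across adolescence can be expected to carry some information about age. Adjusting for age as a main effect removes the association of age with the outcome. It does not remove a difference in treatment effect between younger and older girls. If such a difference exists and the index is correlated with age, the index-by-arm term picks up part of it.

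Randomisation does not help. It protects the comparison of arms, not the attribution of an interaction to one of two correlated characteristics of the girl.

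What is at stake is the reading of Aim 4. Its output is a candidate neurodevelopmental moderator for later work. If age would explain the same pattern, the finding is of a different kind, and age is known for every girl without a scan.

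**Working it through.** **The plan's own figure.** The documents give no power or error rate for Aim 4. The nearest figure is power of .81 for the Aim 1 slope (N = 123, d about .45, 10% missing). A simple two-sided comparison of means gives .704 with no missing data and .658 with 10% missing. If covariates or repeated measures explain about 30% of variance, the 10%-missing figure rises to .808. The growth-model inputs are not given, so .81 can be neither confirmed nor called wrong. It does not bear on Aim 4.

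**Inputs from the documents.** n = 25; eligible ages 13 to 18; 1:1 allocation; alpha .05 (taken as two-sided); age adjusted for as a main effect.

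**Assumed, because the documents are silent.** g, the change in the arm effect (in outcome SD) per SD of age; r, the correlation of index with age. True brain moderation is set to zero.

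**Formula.** With age moderation only, the expected index-by-arm coefficient when age by arm is left out is about r × g:
- r = .4: .4 × .50 = .20
- r = .6: .6 × .50 = .30
- r = .8: .8 × .50 = .40

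**Simulation.** n = 25, one continuous outcome with residual SD 1, age uniform over the eligible range and standardised, least squares. This simplifies the three-wave growth model. With g = .50:

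| r | Planned model: mean | SD | RMSE | False positives | With age by arm: mean | SD | RMSE |
|---|---|---|---|---|---|---|---|
| .4 | .20 | .48 | .52 | 7% | about 0 | .53 | .53 |
| .6 | .31 | .48 | .57 | 10% | about 0 | .60 | .60 |
| .8 | .40 | .48 | .62 | about 14% | about 0 | .82 | .82 |

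The planned-model RMSE follows from bias and SD; for r = .6, √(.31² + .48²) = .57. With age by arm included, the false-positive rate was about 5%.

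**Other values of g.** A separate run at n = 25 gave these false-positive rates without age by arm:
- g = .25: 5.2% (r = .3) to 7.1% (r = .8)
- g = .45: 5.9% (r = .3) to 12.4% (r = .8)
- g = .90: 9.0% (r = .3) to 33.2% (r = .8)

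With r = 0 or g = 0 the rate stays at about 5%. With age by arm included it was 4.4–6.0% throughout.

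**Power for a true brain moderation at n = 25.** For .45 per SD, power falls from about 16% in the planned model to 13%, 11% and 9% in the age-adjusted model at r = .5, .7 and .8. For .90 per SD it falls from about 48% to 36%, 27% and 20%.

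**Age by arm in the full sample.** With equal arms and age in SD units, the standard error is about √(4/123) = .18. For g = .50, .50/.18 = 2.77, so approximate power is Φ(2.77 − 1.96) = .79; simulation gave .77, against .20 at n = 25. For g = .25, Φ(1.39 − 1.96) = .28. These figures allow for no missing data.

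**The case against.** The strongest reply is that little is claimed here. Aim 4 is exploratory, its model is described in one sentence among examples, and an age-by-arm term is unspecified, not excluded. The bias needs two conditions that the documents do not establish. The indices are defined only by reference to earlier studies, so whether they are already age-adjusted is not stated. An assumed g of .50 is also larger than the whole planned intervention effect of about .45, and at g = .25 the false-positive rate is close to nominal. All of this stands. It makes the point conditional and lowers its weight.

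A second reply is that age-related maturation is brain development, so a total effect of maturation is a legitimate target. That also stands, and it is a reason to keep the planned model. It does not make that model able to say which of the two characteristics is responsible.

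A third is that adjustment costs more than it gains as a replacement: the adjusted estimate has equal or larger RMSE in every setting tabulated. That is correct, and it is why the adjusted model belongs beside the planned one.

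A reader might infer that an age difference in SHARP's effect will be reported as brain moderation. The documents do not support that. Even with g = .50 and r = .8, about 86% of trials would show no significant brain-by-arm term. The usual consequence is a biased, non-significant estimate.

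**Conclusion.** The point holds in conditional form: as written, Aim 4 does not separate age from brain maturation as moderators, and a brain-by-arm estimate could reflect age. The bias is about r × g, so it vanishes if either is zero. The .20 to .40 range and the false-positive rate of about 7–14% rest on the assumed g = .50, on r between .4 and .8, on a single continuous outcome, and on scanned girls who span the eligible ages. If their ages cluster narrowly, an SD of age covers fewer years, and both r and g may be smaller.

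This is an inexpensive improvement to an exploratory aim. It limits what Aim 4 can conclude and leaves Aims 1 to 3 untouched.

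**What to change.** In the Aim 4 paragraph of the SAP:

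1. Keep the planned brain-by-arm model.
2. Test age by arm in all 123 girls, where no scan is needed. A non-significant result there should not be read as absence of age moderation, given power of only about .28 for g = .25.
3. Report beside the planned model a sensitivity model with both age by arm and index by arm, giving estimates and confidence intervals for both. Residualising the index on age as well is redundant: once age and age by arm are in the model, it leaves the index-by-arm coefficient unchanged.
4. Attribute moderation to brain development as distinct from age only if the age-adjusted term supports it.
5. State that 25 girls can rarely separate the two (power about 9–13% for a moderation of .45 per SD at r = .5 to .8).

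The cost is SAP wording and one further model per outcome; age is already held as an eligibility item. The statistical cost is precision: the SD of the index-by-arm estimate rises from about .48 to .53, .60 and .82 at r = .4, .6 and .8.
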